## 2.3 Clinical Data to Date

### 2.3.1 Development and Implementation of the DSM-H.

As part of [name] Palliative Care Research Center Career Development Award, [name] and [name] (Mentor) developed the DSM-H. The development utilized the NIH ORBIT Model for Behavioral Intervention Development and later on the Structural Model for Caregiving Stress. The DSM-H focuses on assisting skilled HHC clinicians to identify and managing behavioral symptoms associated with dementia, and work as a team with the primary care provider and informal caregiver. In this initial trial, two registered nurse, physical therapist, and occupational therapist educators (6 total educators) at the study site were trained as "champions" and received 14 hours of in-person, case based interprofessional instruction over two days in dementia care; the remaining 209 RNs, PTs, and OTs received 4.5 hours of modular, on-line interactive learning training. Champions served as resources for other clinicians and helped ensure smooth implementation and completion of the program. In addition to the education, participants were provided with resources and workflow changes including previously validated assessment tools for assessing and managing symptoms in PWD, and care plans based on evidence based practice for PWD. As a measure of program evaluation, Drs. [name] and [name] developed the Dementia Symptoms Knowledge and Attitudes Survey to be utilized as a pre- and post-test. The survey incorporates three well-validated instruments for assessing clinician knowledge and attitudes regarding pain, depression and agitation in PWD, with an investigator-derived set of four questions about confidence in treating each of these symptoms in PWD. The survey had an excellent internal consistency in HHC clinicians (Cronbach

CONFIDENTIAL

This material is the property of the NYU School of Medicine and Langone Medical Center. Do not disclose or use except as authorized in writing by the study sponsor

alpha=.94) and took an average of 15 minutes to complete. In our sample of 209 clinicians, we found significant improvements in knowledge, attitudes and care confidence in treating PWD following program completion that varied by specialty. Overall, clinicians showed the most improvement in knowledge (20.9%) and confidence (27.1%) in managing BPSD from baseline with additional gains in knowledge (14.8%) and confidence (36.1%) in managing depression and knowledge (5.9%) and confidence (26.5%) in managing pain ( $p<.0001$ ). Additionally, on the post-test evaluation, 97% of RNs and 100% of PTs and OTs stated the education was highly applicable to their work setting and helped them care for patients. ***Therefore, the DSM-H is an evidence-based practice integrated multi-component intervention that has shown improved clinician knowledge, attitudes and confidence in treating PWD.***

### 2.3.2 Pilot testing

Based on feedback from this initial trial of the DSM-H, [name] refined the clinical education programs to reduce pharmacology content and increase content on recognition of dementia and non-pharmacologic management and working with caregivers. Drs. [name] and [name] performed a site controlled trial of the DSM-H at 2 divisions of a large HHC agency and retrospectively collected OASIS and chart data for PWD on admission and at the first 60-day re-certification or discharge from HHC. Overall, during the study period 158 PWD were seen by the control site and 174 by the intervention site. Overall, patients were older, primarily spoke English or Spanish, were either Medicare or dual Medicare/Medicaid insured, and were admitted either from home or the acute care setting (See Appendix A). There were fewer black/African American participants in the control, the only clinically significant difference (34.2% vs 51.7%;  $p=.0002$ ). Overall, we found in multivariate analysis that recognition of pain, depression, and behavioral symptoms, were all clinically and statistically significantly higher in the intervention group, and there were significantly increased odds of analgesics use (OR=2.01;  $p<.05$ ) and decreased odds of antipsychotic use (OR=0.53;  $p<.05$ ) in the intervention cohort. ***These results show the DSM-H has the potential to be improve patient care and the QOL of PWD receiving HHC.***

### 2.4 Rationale

While significant focus has been placed on implementing solutions for use in the acute care, nursing home, and primary care settings, few studies have focused on improving symptom management and caregiving training for PWD through HHC. Drs. [name] and [name] have adapted interprofessional, evidence-based practices, from other settings to HHC, creating the DSM-H. The DSM-H has been piloted with over 600 HHC clinicians. It is a multi-component performance improvement program that consists of clinician training, patient- and family-centered assessment instruments, patient-caregiver dyadic centered care plans, a BPSD assessment and treatment algorithm, and caregiver teaching sheets. The pilot studies have shown improved clinician knowledge, confidence and attitudes, and pain and BPSD recognition and management. We therefore seek to test the efficacy of the DSM-H in a behavioral phase III cluster randomized controlled trial.

### 2.5 Potential Risks & Benefits

#### 2.5.1 Known Potential Risks

The performance improvement program itself is inherently not risky (**minimal risk**) as it is an implementation of evidence-based practices. The primary risk to patients and caregivers in this study is the emotional nature of the questions from study data collection, which is solely an immediate risk. While the measures being used are all evidence based and thoroughly tested, they cover issues such as increased severity of dementia, depression, agitation, burden and quality of life that could create emotional problems. This will be minimized by implementing a thorough training plan and manual for the research assistant performing the assessments, laying out responses that should be provided to sensitive questions, ensuring that the assessment instruments are uniformly administered, and methods and contact numbers for referrals in case of any emotional disturbance related to the research. We are

CONFIDENTIAL

This material is the property of the NYU School of Medicine and Langone Medical Center. Do not disclose or use except as authorized in writing by the study sponsor

currently performing a study using these instruments and have a set training for research assistants administering these instruments. Additionally, other peer reviewed studies have not reported any adverse reactions to these instruments, so we see this risk as minimal. Additionally, we will perform an informed consent with both the caregiver and PWD if able, or patient surrogate if unable, so that they have full awareness of the purpose of the project, potential types of questions, and the voluntary nature of the study. The second risk is loss of confidentiality. We minimize the risk by maintaining the data in a secured fashion (see [section 11](#)). This vulnerable population is included as the focus of the research is in improving the quality of care they receive.

As the potential risks are minimal and there are potential direct benefits to subjects in the performance improvement cohort, including improved PWD and caregiver QOL and symptom management, and reduced utilization, the potential benefits of this study far outweigh the minimal risks to this study. The value in this study is that if efficacy is found, the intervention can be created into a product that is disseminated to some of the over 12,000 active HHC agencies in the country to improve the quality of care in these settings and QOL for hundreds of thousands of PWD-informal caregiver dyads.

## 2.5.2 Known Potential Benefits

Potential benefits to patients in the intervention includes improved quality of care and quality of life, including reduction in pain and BPSD, and reduced healthcare utilization, which could lead to lower out of pocket costs. For caregivers receiving care from care teams who are part of the performance improvement program, potential benefits include reduced depression, burden, and improved physical and mental health. These hypothesized benefits are based on our preliminary data found in section 2.3.2.

## 3 Objectives and Purpose

### 3.1 Primary Objectives

***Aim 1: Measure the effects of the DSM-H on quality of life and symptom severity in the PWD.***

H1: PWD cared for by a HHC team utilizing the DSM-H performance improvement program will show reduced symptoms and improved ratings of pain, BPSD, and caregiver-rated QOL at the end of the first 60-day HHC certification period compared to the control (usual care) group.

The primary outcome of Aim 1 is caregiver rated QOL. It will be measured using the Quality of Life-Alzheimer's Disease.

***Aim 2: Assess the effects of the DSM-H on quality of life, and physical and mental health in the informal caregiver of the PWD.***

H2: Informal caregivers of PWD cared for by a HHC team utilizing the DSM-H performance improvement program will show reduced ratings of burden, and depression, and improved functional health and well-being at the end of the first 60-day HHC certification period compared to the control (usual care) group.

The primary outcome of Aim 2 is informal caregiver QOL. It will be measured using the Caregiver-Targeted Quality of Life Measure.

***Aim 3: Assess the effects of the DSM-H on healthcare utilization in the PWD.***

H3: PWD cared for by a HHC team utilizing the DSM-H performance improvement program will show a reduction in emergency room visits and hospital admissions compared to the control (usual care) group, and a greater number of outpatient visits.

The primary outcomes to be measured are the number of emergency room visits and hospital admission rates of the PWD at 30 and 60 days. It will be measured through interviews with the informal caregiver using the Resource Utilization Inventory.

CONFIDENTIAL

This material is the property of the NYU School of Medicine and Langone Medical Center. Do not disclose or use except as authorized in writing by the study sponsor  
 Interventional Template Version: 28 APR 2017

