The legal surrogate will be verified by either the HHC agency or through written documentation. Should they not have written documentation of being an appointed surrogate, the law of the state of residence will determine the priority order for determining the surrogate, which is as follows:

Florida: spouse, adult child, parent, adult sibling, close friend

New Jersey: spouse, adult child, parent, sibling, close friend

Utah: spouse, adult child, parent, sibling, grandchild, grandparent, individual who is healthcare proxy

Because PWD in HHC are primarily homebound, tend to receive HHC for at least 60 days, with follow-up is provided through scheduled home visits, we do not anticipate significant retention problems. Additionally, the study burden is minimal, requiring approximately an hour per dyad at baseline and 60-days, and 20 minutes at the 15 and 30 days. Study staff will obtain detailed contact information for the PWD, caregiver, and where applicable proxy, will schedule the follow-up visits at the initial visit, email or text the visit schedule to the caregiver (based on caregiver preference; no PHI or PII included, see templates), and call 4 days and 1 day prior to each follow-up appointment to confirm and/or reschedule.

The greatest risks to retention are re-hospitalization and institutionalization, either for short-term post-acute rehabilitation after a re-hospitalization or long-term institutionalization for ADRD. Subjects are not required to attend the intermediate and final visits together. Efforts to accommodate the subjects' schedules will be considered in data collection. Phone interviews with the PWD and caregiver to collect participant survey data will occur for all time points. If both subjects are unavailable to complete an intermediate visit, the visit will be recorded as missed. To maintain subject retention, subjects will be terminated from the study only if the caregiver, as respondent, does not complete visit four.

Dyads will be enrolled starting in month 6 of year 1 and continuing through month 9 of year 4 (3 years, 3 months). Follow-up will continue through Month 2 of year 5. The investigators therefore anticipate recruiting 9 new dyads per month at all sites throughout the 4 years, with 5-6 through the VNA Health Group, 2-3 at the University of Utah and 1-2 at University of Miami.

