#### **5.7.2 Handling of Participant Withdrawals or Termination**

Given the minimal risk nature of this study, individuals who chose to withdraw from the study will not continue to be followed in any form. We have factored in a 15% study non-completion rate and anticipate recruiting 345 dyads to meet the 300 dyads required study participants. Subjects will not be disenrolled based on data related issues. If subjects are unable to attend intermediate visits (Visit 2 and/or 3), those visits will be counted as missed. If the caregiver does not complete visit four, both subjects will be terminated from the study.

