##### **Visit 3 (Day 30+/-3)**

The following surveys will be administered for visit three:

*Surveys administered to the PWD are indicated by their QDRS score:*

- PAINAD (If QDRS >12)
- FAM-CAM
- BPI (If QDRS≤12)
- NPI-Q
- Katz ADLs and Lawton iADLS (through the QOL-AD)
- Resource Utilization Inventory
- Non-instrumented: Medication Record and Usage, Resource Utilization Inventory, AE and SAE, COVID-19 questions

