### 7.2.6 Collection of Home Health Record

Following the final study visit, the home health agency will extract the PWD subject's health record, including OASIS documentation, symptom scores, assessment information, and administrative visit information.

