### 7.2.7 Withdrawal/Early Termination Visit

Should individuals withdraw from the study for any reason, we will attempt to ask for the reason and ask if any SAE or AE have occurred if the PWD/caregiver are reachable. We will also if withdrawal is for non-communication with the study team we will review the HHC medical record to ascertain if there was an SAE or AE.

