## 10.4 Description of Statistical Methods

### 10.4.1 General Approach

Data Analysis will be performed using SAS 9.4. We will perform statistical tests to examine baseline differences between the quality improvement program and control groups. We will then perform unadjusted comparison of both primary outcomes (patient and caregiver quality of life, emergency room visits) and secondary outcomes (pain, BPSD, delirium, caregiver depression burden, and burnout, hospital and emergency room admissions) between groups. We will focus on the endpoint measure for quality of life, and 30 and 60-day outcomes for emergency room utilization. For primary and secondary outcomes, we will perform a time trend analysis using a mixed effects linear model (PROC MCM). Mixed effects regression is used to analyze longitudinal data with repeated measures accounting for intra-individual and group clustering. We intend to use multivariate mixed effects regression modeling as opposed to traditional linear modeling or ANOVA in order to control for unobservable confounding variables that are constant over time but differ across PWD and/or caregivers. For both primary and secondary outcomes, we will then repeat the above analyses adjusting for baseline variables as covariates for a more efficient measurement of the effects of the quality improvement program. We will also perform correlation analyses to explore the relationship between pain and BPSD, and PWD and caregiver QOL through plotting scores over time and then if a significant correlation is present through adding to our mixed effect model. For utilization data, we will perform logistic regression to examine whether the patient is more or less likely to have a hospitalization or ER visit compared when receiving the quality improvement program at 30 and 60 days. We will then perform a Poisson Count Regression to compare the total number of hospitalizations and ER visits at each timepoint. In these models we will utilize a random effect to measure for clustering.

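### The Aim 3 primary endpoint rests only on caregiver interviews at visits 3 and 4, with no recall rule or second source for events in dyads that miss one

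*Combined protocol and SAP*

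**What the plan says.** Section 3.1 (Aim 3) defines the primary outcomes as "the number of emergency room visits and hospital admission rates of the PWD at 30 and 60 days" and names one source: "It will be measured through interviews with the informal caregiver using the Resource Utilization Inventory". The visit 3 list in section 7.2 includes it ("Non-instrumented: Medication Record and Usage, Resource Utilization Inventory, AE and SAE, COVID-19 questions"), and so does the visit 4 list in 7.2.5. The visit 2 list does not. Table 2 also ticks day 0, which the visit 1 list omits.

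On missed visits, section 5.7.2 says: "If subjects are unable to attend intermediate visits (Visit 2 and/or 3), those visits will be counted as missed". The same section terminates both members if the caregiver does not complete visit 4. Section 8.8.2 replaces withdrawals with completed cases, and section 10.5 recruits to 15 completers per cluster. Section 5.4 states: "The greatest risks to retention are re-hospitalization and institutionalization".

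Section 10.4.1 plans logistic regression for any event, then a Poisson model to "compare the total number of hospitalizations and ER visits at each timepoint", with a random effect for clustering. It gives no rule for a missed interview. Section 10.4.3 compares retained with lost subjects but recovers none of their events.

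Three other routes can bring an admission to light:
- Section 8.1 includes hospitalization among monitored events, and section 8.3 asks about AEs and SAEs at each visit, back to the previous visit, with time of onset.
- Section 7.2.7 covers withdrawal for non-communication: "we will review the HHC medical record to ascertain if there was an SAE or AE".
- Section 7.2.6 says that after the final visit "the home health agency will extract the PWD subject's health record".

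None of the three is linked to Aim 3.

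**The concern.** The event that Aim 3 counts is also one that the protocol expects to disrupt follow-up. If an admission makes the next caregiver interview less likely, whether the outcome is recorded depends on the outcome itself. A logistic or Poisson model cannot restore events that nobody asked about.

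There are two ways to lose them. If visit 3 is missed, the 30-day outcome has no RUI. The 60-day total may then be short as well, because the documents do not state the RUI recall period or tell visit 4 to cover days 0 to 30. If visit 4 is missed, the dyad is terminated and another completer takes its place.

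At stake is a primary outcome judged against a small target: section 4.2.1 calls a 10% reduction at 60 days a positive result.

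**Working it through.** **The plan's own figures.** Section 4.2.1 equates the 10% reduction with 63.8 fewer admissions and 220 fewer ER visits per 1000. Read as a relative reduction, the base rates are 63.8/0.10 = 638 admissions and 220/0.10 = 2200 ER visits per 1000. Section 10.5 gives 300 × 1.15 = 345 dyads for 15% dropout. No sample size is given for Aim 3, and no loss rate by hospitalization. Every loss rate below is therefore an assumption.

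**Visit 3 loss, 30-day outcome.** Let p be the true admission risk, and let m_a and m_n be the proportions of admitted and non-admitted dyads without a visit 3 RUI. Among dyads interviewed:

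observed risk = p(1 − m_a) / [p(1 − m_a) + (1 − p)(1 − m_n)]

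Assume p = 0.20 control and 0.18 intervention (true risk ratio 0.90), with m_n = 0.05 in both arms.

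- Control, m_a = 0.30: 0.140/(0.140 + 0.760) = 0.156, which is 22% below 0.20.
- Intervention, m_a = 0.30: 0.126/(0.126 + 0.779) = 0.139; observed ratio 0.895.
- Intervention, m_a = 0.20: 0.144/(0.144 + 0.779) = 0.156; observed ratio 1.00.
- Intervention, m_a = 0.40: 0.108/(0.108 + 0.779) = 0.122; observed ratio 0.78.

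The true odds ratio is (0.18/0.82)/(0.20/0.80) = 0.878. With equal m_a the observed value is (0.126/0.779)/(0.140/0.760) = 0.878, unchanged. Control risks of 15% to 25% give ratios of 1.01 to 1.00 in the third case and 0.78 to 0.79 in the fourth.

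With 345/2, about 172 dyads per arm, admitted dyads number about 0.18 × 172 = 31 to 0.20 × 172 = 34. A ten-point gap is then about three dyads.

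**Visit 4 loss, 60-day outcome.** Assume 15% overall loss D, with admitted dyads k times as likely to be lost. Then d_n = D/(1 − p + kp) and d_a = k·d_n. For p = 0.30 and k = 3: d_n = 0.15/1.6 = 0.094 and d_a = 0.281. The observed risk is 0.30 × 0.719/0.85 = 0.254, which is 15% too low, and 345 × 0.30 × 0.281 = 29 admitted persons leave the outcome.

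| Assumed 60-day risk | Understated at k = 2 / 3 / 5 |
|---|---|
| 15% | 13% / 23% / 38% |
| 30% | 10% / 15% / 23% |
| 47% (= 1 − exp(−0.638)) | 6% / 10% / 13% |

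Across the table, about 13 to 42 admitted persons per 345 are lost. If that loss is equal by arm, the odds ratio again does not move (0.863 true and observed at p = 0.30).

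Now let loss among the admitted be 25% in control and 35% in intervention, with 8% among the non-admitted. A true null then appears as odds ratio 0.65/0.75 = 0.87 and risk ratio 0.88 to 0.92. Over the ranges tried (control loss among the admitted 15% to 35%, risk 15% to 47%), a gap of about 7 to 14 points turns a null into a risk ratio of 0.90.

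**Limits.** The first set is a 30-day scenario and does not compute the 60-day criterion. The second concerns a different mechanism, so it does not confirm the first. Neither is an estimate for this trial.

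**The case against.** The strongest case against is substantial, and much of it stands.

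A reader might infer that admissions are recorded nowhere but in the RUI. The documents do not support that. Sections 8.1 and 8.3 bring hospitalization into SAE questioning, with a look-back to the previous visit and an onset time, so an admission before a missed visit 3 could be reported at visit 4. What remains is that this log is not tied to Aim 3. Two of its three follow-up contacts are the RUI visits themselves. The list of monitored SAEs in section 8.1.1 names a suicide attempt and deaths but not hospitalization. ER visits without admission are not clearly covered.

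A reader might also infer that a hospitalized patient means a lost interview. Section 5.4 says otherwise: the caregiver answers, by phone, the pair need not attend together, and an intermediate visit is recorded as missed when both are unavailable. This lowers the risk but does not remove it, since the same section still ranks re-hospitalization among the greatest retention risks.

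Third, the RUI recall window is unknown, not shown to be too short. The instruments and study manual are separate attachments. Loss of days 0 to 30 from the 60-day total is therefore a possibility.

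Fourth, bias in the comparison needs an arm difference that no document reports, and the research assistants are blinded. In the 30-day scenario, with 150 per arm and design effect 1 + 14 × 0.05 = 1.7, the standard error of the log risk ratio is about 0.31. The assumed shift, ln(1.003/0.895), is about 0.11. Sampling error would dominate, although the shift is as large as the targeted effect.

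Finally, section 7.2.6 does not list ER visits or admissions among the extracted items, and the program itself may change documentation in intervention teams. A second source used only for dyads with missed visits could therefore add an arm-dependent error. The fix allows for this.

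**Conclusion.** The point holds as a gap in measurement. A primary endpoint has one named source, given at two follow-up contacts. Neither a recall window nor a rule for a missed contact is stated, and the protocol expects the endpoint event to threaten follow-up. Events in dyads that miss an interview can be lost.

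The consequence depends on the pattern of loss. If it is equal by arm, observed rates and precision fall and the odds ratio is essentially unchanged. If loss among admitted dyads differs by arm, the comparison is biased, and in the assumed scenarios gaps of roughly 7 to 14 points are on the scale of the 10% target. The documents give no rates from which to say whether such a gap will occur. It would go too far to conclude that the endpoint removes its own events, or that the Aim 3 result will be wrong by a stated amount.

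The change is still worth making, because it is cheap and because events not asked about may be unrecoverable later.

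**What to change.** 1. In the visit 3 and visit 4 procedures, state that the RUI covers every ER visit and admission since the last completed RUI contact (since visit 1 if visit 3 was missed), with dates, so that the 30- and 60-day counts can be rebuilt.
2. In Aim 3 and section 10.4.1, name the SAE log and the extracted agency record as second sources. Apply them to all dyads in both arms, not only to those with missed visits, because documentation may differ by arm. Report the result as a supporting or sensitivity analysis, and include dyads terminated for a missed visit 4 where consent allows. Confirm first which events the record holds. The benchmark in section 4.2.1 cites OASIS-based agency reports, which suggests that it can hold them.
3. Extend the record review in section 7.2.7 from AEs and SAEs to Aim 3 events.
4. Reconcile section 8.1, which monitors hospitalization, with the shorter list in section 8.1.1. This decides whether the SAE log can serve as a backup.

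Cost: longer recall for caregivers who missed visit 3, and modest extra abstraction from records that the trial already obtains.
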